7.3 Other research statistics

The other research outcomes encompass the detection rate of AN by FIT, miR-92a, and their combination.

7.4 Statistical methods

A variety of categorical data analysis methods will be used to analyze the results from the miR-92a, FIT and FIT + miR-92a results. Binomial proportions and exact 95% CI summarize sensitivity and specificity across categories. According to the study design, FIT and miR-92a from the same subjects were considered as a paired design, and the exact McNemar's test was used to compare the differences of DR, PR, Se and Sp between these two groups. Given the susceptibility of PPV to confounding factors like prevalence and subject characteristics, the GEE (Generalized Estimating Equations), which is based on McNemar's test, was utilized to compare the differences in PPV between the two groups.

8. Ethical issues

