2.3 Research content

The study was conducted at Shenzhen People's Hospital (SZH) (head unit), Shenzhen Bao'an District Hospital of Traditional Chinese Medicine (BAT) and Tianjin Nankai Hospital (NKH). 16,505 subjects were enrolled according to the inclusion and exclusion criteria. During the recruitment process, the researchers will fully introduce the content, risks and value of the study to the subjects. Subjects will sign an informed consent to participate in the study after they have been fully informed of the content, risks and benefits of the study and their questions have been answered. A short interview using the CRC risk questionnaire will be conducted and a stool sample collection kit will be given to the subjects. One stool sample will be collected according to the stool sample collection instructions and returned to the clinical site. The sample will be used for fecal-based miR-92a and FIT (9. Instructions for stool sample collection). Colonoscopy and/or pathology will be performed on subjects with positive fecal-based miR-92a and/or FIT. Some screen-negative individuals will also be randomly selected for colonoscopy and/or pathological examination. The study will analyze the performance of FIT, miR-92a and their combination in the screening of CRC and AA [advanced neoplasia (AN)] using colonoscopy and/or pathological findings as the gold standard.

3. Research target

To analyze the performance of FIT and fecal-based miR-92a and their combination for AN, and to evaluate the performance indicators and form an early screening and prevention strategy for people at average risk of CRC.

4. Research methods

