6.1 Subjects enrolled

Subject enrolment will be initiated after the project has been approved by the ethical review committee. The researchers will determine whether to recruit subjects based on the inclusion and exclusion criteria, explain the study in detail to those who meet the enrolment criteria and are interested in participating in the trial, and answer all questions raised by the subjects to ensure that they are fully aware of the content of the study, the risks, benefits and other relevant information. The subject signs the informed consent to participate in the study. Subjects have the right to withdraw from the study at any stage after successful recruitment. Subjects may contact the study leader to inquire about test results or to request withdrawal.

The researcher will use the CRC risk questionnaire to interview the subjects after they have signed the informed consent to participate in the study. One copy of the informed consent will be retained by the subject after signing, and the other copy will be kept on file together with the subject's information and code. The subject code will be used as the unique identification number of the subject, which will be used to identify the samples, laboratory test data, and summarize the required information to meet the needs of information query and verification. Stool samples will be taken from the subjects.

11

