6.6.1 Subjects tested positive for fecal samples

The researchers actively followed up with positive subjects, i.e., fecal miR-92a positive subjects, FIT positive subjects, miR-92a + FIT positive subjects, and provided education on bowel health and CRC prevention while facilitating the timely completion of colonoscopy.

The researchers counted the results of fecal samples in batches and contacted the subjects with positive fecal miR-92a and/or FIT tests to follow up with them to receive the colonoscopy and to make an appointment for the colonoscopy. After confirming the subject's acceptance of the colonoscopy and setting a date for the colonoscopy, the researcher contacted the subject again to follow up with him/her to learn about the colonoscopy precautions and to remind him/her to pick up the medications and materials needed for the bowel preparation. The researcher retrieved the colonoscopy report and pathology results in a timely manner after the subject completed the colonoscopy.

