- After clicking on the model to execute the function, drop down the cell and generate random data.
- Select the data cells in column B, right-click the mouse and select "Sort" in the "ascending".
- By expanding the selected region, the data in column A can be redistributed randomly.
- Select the first three rows of the worksheet, select the toolbar in the "data" menu in the "combination" option, read
 the number obtained that is randomly selected subjects.
- Initiate a follow-up telephone call with three randomly selected subjects to follow up on the completion of the colonoscopy. If any of the subjects refused to undergo colonoscopy, the randomized follow-up subjects were deferred.

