8.1.3 Subject benefits

Through enrolment in the study, subjects will receive 100 RMB as compensation for travelling expenses. Subjects will be offered a free fecal-based miR-92a test and FIT with result interpretation by a professional technician and possible follow-up management to improve knowledge of CRC prevention and early detection of possible risk of intestinal lesions.

Subjects will be offered a free colonoscopy if they have a positive fecal-based miR-92a test or FIT. If lesions are found, samples of the lesions will be taken for histopathology examination. Subjects can choose to undergo either plain or painless colonoscopy. The cost of colonoscopy (plain or painless) and histopathology examination will be borne by the company.

Subjects will be offered free colonoscopy when they have a negative fecal-based miR-92a test or a negative FIT test but are contacted by the investigator at random. If microscopic lesions are identified, they will be sampled for histopathology examination. Subjects may choose to undergo either a plain colonoscopy or a painless colonoscopy. The cost of colonoscopy (plain or painless) and histopathology examination will be borne by the company.

Subjects will not be offered a free colonoscopy if they have a negative fecal-based miR-92a test or a negative FIT test but are not contacted by the investigator at random.

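### The McNemar comparison of FIT and miR-92a on sensitivity, specificity and detection rate needs equal colonoscopy uptake in the two discordant groups within each disease class, and section 7.4 does not guard against unequal uptake

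*Protocol*

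**What the plan says.** Section 7.4 treats the two stool tests as paired within subject and names one method for four measures: "the exact McNemar's test was used to compare the differences of DR, PR, Se and Sp between these two groups". It sets no condition on who reaches colonoscopy and does not say how positives without colonoscopy are handled.

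On verification, section 2.3 states: "Colonoscopy and/or pathology will be performed on subjects with positive fecal-based miR-92a and/or FIT". It adds: "Some screen-negative individuals will also be randomly selected for colonoscopy and/or pathological examination". Both discordant groups (FIT-only and miR-92a-only positives) are therefore meant to be verified in full, and double-negatives by sampling.

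Verification is voluntary and comes after the stool result:

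- Section 6.6.1 moves to the preparation call only "After confirming the subject's acceptance of the colonoscopy and setting a date for the colonoscopy".
- Section 6.1: "Subjects have the right to withdraw from the study at any stage after successful recruitment". Also: "Subjects may contact the study leader to inquire about test results or to request withdrawal".
- Section 8.1.3: "Subjects will be offered a free fecal-based miR-92a test and FIT with result interpretation by a professional technician".
- Section 6.6.2 foresees refusal among sampled negatives: "If any of the subjects refused to undergo colonoscopy, the randomized follow-up subjects were deferred".

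Section 7.1.1 requires a colonoscopy-confirmed diagnosis before a subject can be a true positive. An overall compliance rate is a planned indicator (1.3, 7.1.3), but no attendance figure is given for any result pattern. The 5% dropout in section 5.5 is not split by test result.

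**The concern.** McNemar's test asks whether the two discordant counts differ by more than chance. If the tests are equally good but one discordant group attends colonoscopy more often, that group supplies more verified subjects and the counts differ for a reason unrelated to accuracy. The test whose positives attend more looks more sensitive, because more of its AN is confirmed. It also looks less specific, because more of its false positives are confirmed.

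The condition has to hold within disease class: equal attendance among discordant subjects with AN for sensitivity and detection rate, and equal attendance among discordant subjects without AN for specificity. Equal attendance overall is not enough.

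The sampling of double-negatives is a separate matter. They are concordant, so they do not enter McNemar, and reweighting them alone cannot repair an imbalance among positives. At stake is the head-to-head statement that one test is better than the other.

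**Working it through.** **The protocol's own figure.** Section 5.5, for CRC sensitivity: 1.96² × 0.9 × 0.1 / 0.09² = 42.68 cases, and 42.68 / 0.003 = 14,228. This reproduces. The calculation sets precision for miR-92a sensitivity; it gives no power or attendance assumption for the FIT v miR-92a comparison.

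**Inputs.**
- From section 5.5: prevalence of CRC 0.3% and AA 3%, so AN 3.3%. 14,228 × 0.033 ≈ 470 with AN, and 14,228 − 470 = 13,758 without.
- Assumed, because the protocol gives neither FIT accuracy nor test overlap: the tests are truly equal, with a share q of subjects in each discordant cell. q is 10% to 25% among AN. Among non-AN, q is 5% to 9%; 9% is what two independent tests with 90% specificity give (0.10 × 0.90).
- Assumed attendance in the two discordant cells: 80% in one; 80%, 75%, 70% or 60% in the other.

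**Formula.** Verified discordant counts have expectation b = M·q·a₁ and c = M·q·a₂, with M the number in the disease class. The exact two-sided p-value is min{1, 2·P[Bin(b+c, ½) ≤ min(b, c)]}. With equal tests, the chance that a verified discordant subject falls in the first cell is a₁/(a₁+a₂), not ½: 0.516 at 80/75, 0.533 at 80/70, 0.571 at 80/60.

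**Example.** AN, q = 20%: 470 × 0.20 = 94 true cases per cell. At 80/60 about 75 v 56 are verified. Non-AN, q = 9%: 13,758 × 0.09 ≈ 1,238 per cell. At 80/70 about 991 v 867 are verified, a normal deviate of about 124/√1,858 = 2.9.

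**False rejection at a nominal 5%, tests truly equal** (50,000 simulated trials per setting):

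| Attendance | AN sensitivity, q 10–25% | Specificity, q 5–9% |
|---|---|---|
| 80 v 80 | about 4% | about 5% |
| 80 v 75 | about 4–6% | about 17–29% |
| 80 v 70 | about 7–13% | about 56–82% |
| 80 v 60 | about 18–42% | about 100% |

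At the larger gaps almost all rejections are in one direction. Specificity suffers more because its discordant cells are many times larger.

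**Second set of assumptions.** With the 15,586 subjects of section 5.5 and two independent tests of 80% sensitivity, there are 514 AN and 514 × 0.16 ≈ 82 per discordant cell. False rejection for sensitivity is 10.9% at 80/70 and 30% at 80/60. For CRC alone, 15,586 × 0.003 × 0.09 ≈ 4 per cell, and false rejection stays at about 5% or below even at 90/60.

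**Would weighting help?** Weighting verified subjects by the inverse attendance of their result pattern brings the error rate back to about 5%, provided attendance is unrelated to disease within a weighting cell.

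**Why double-negatives must be weighted too.** Once the analysis estimates a difference, double-negatives are in its denominator. Assume false-positive rates of 5% (FIT) and 10% (miR-92a), independent errors, all positives scoped and 20% of double-negatives scoped. Among non-AN the cells are 0.5% both positive, 4.5% FIT-only, 9.5% miR-92a-only and 85.5% double-negative. The true specificity difference is 9.5 − 4.5 = 5 points. With double-negatives left unweighted the denominator is 0.5 + 4.5 + 9.5 + 0.2 × 85.5 = 31.6, and the difference becomes 5.0/31.6 ≈ 16 points.

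**The case against.** Exact McNemar is a standard choice for paired tests, and section 2.3 sends positives on either test to colonoscopy, so both discordant cells are verified by design. Several features favour equal uptake. Willingness to be scoped is an inclusion criterion (5.2). Section 6.6.1 gives every kind of positive the same contact, education and reminders. Colonoscopy is free whichever test is positive (8.1.3). Handling of non-attenders could sit in a statistical analysis plan that is not shown.

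Much of this stands. Four stronger readings are tempting, and the document does not support them:

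- *The comparison is biased.* No attendance by result pattern is given. At a five-point gap, AN sensitivity is barely affected.
- *Subjects attend differently because they know which test was positive.* Sections 6.1 and 8.1.3 let subjects ask for results and offer interpretation. Neither says that each positive learns which test triggered the call before deciding.
- *All four measures in the quoted sentence are affected.* PR is not defined in the text shown. If it is the positivity rate, it needs only stool results, and colonoscopy uptake is irrelevant.
- *McNemar should give way to a weighted main analysis.* Weighting brings an untestable assumption of its own, and the size of the problem is unknown until attendance is shown.

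What remains is that the safeguards reduce the risk without ensuring equal uptake, while section 7.4 already fixes the test for sensitivity, specificity and detection rate with no check on its condition.

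**Conclusion.** The point holds as an unguarded risk. For sensitivity, specificity and detection rate, the section 7.4 comparison is valid only under equal verification of the two discordant groups within each disease class, and the protocol makes that verification depend on acceptance after a positive result. Specificity is the exposed measure, since a five-point attendance gap is enough to distort it. AN sensitivity needs a gap of ten points or more before the error rate rises clearly, and CRC alone is little affected. These sizes rest on assumed attendance, assumed overlap between the tests and truly equal accuracy; the document supplies only the prevalences and sample size.

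**What to change.** In section 7.4:

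1. Keep exact McNemar.
2. Report colonoscopy attendance for each of the four FIT/miR-92a result patterns.
3. Add a sensitivity analysis, specified before it is run, of the sensitivity and specificity differences. Weight every scoped subject, sampled double-negatives included, by the inverse of the verification rate in their result pattern (those scoped divided by all tested with that pattern), by coarse age band, sex and site, with a bootstrap confidence interval. Coarse bands matter: nine five-year groups × two sexes × three sites would give 54 strata per pattern.
4. Define DR by its denominator. If it is yield per person screened, non-attendance is part of the quantity and it should stay unweighted.
5. State that if the weighted and unweighted results disagree, neither test will be claimed better.

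The cost is a few sentences and one weighting step. Section 6.7 already puts age, gender, both stool results and colonoscopy findings in the database, and subject sample numbers are assigned by site (8.1.2). Section 1.5 gives the analysis as complete by the end of 2023; if unweighted results have been seen, the weighted analysis should be labelled as added afterwards. The downside is wider intervals, and the assumption that attendance is unrelated to disease within a weighting cell.

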8.1 Risk analysis

8.1.1 Subject risks

Stool samples will be collected non-invasively, using a stool sample kit that allows subjects to collect stool samples in a self-contained and convenient manner. The process of stool sample collection may be psychologically uncomfortable for the subject, but there is no risk to the subject's health. The fecal-based miR-92a test and FIT are performed in the laboratory by professional technicians. There is no risk to the subject's health from the sample testing process.

Subjects will be asked to undergo colonoscopy when they have a positive result for fecal-based miR-92a or FIT or when they have a negative result for fecal-based miR-92a or FIT but are contacted by the investigator on a random basis. Subjects will be offered the choice of a plain colonoscopy or a painless colonoscopy. Subjects will be asked to complete bowel preparation prior to the colonoscopy and may experience discomfort because of evacuating the bowel after taking oral bowel cleansing medications. General colonoscopy is invasive and may pose a risk of bowel perforation or bleeding. Subjects may briefly experience bloating after the colonoscopy due to inflation of the bowel during the procedure.

Painless colonoscopy is invasive and may pose a risk of perforation or bleeding. Subjects may briefly experience bloating after the colonoscopy due to inflation of the bowel during the procedure. A painless colonoscopy will be conducted under general anesthesia before the procedure begins and will continue while the subject remains under general anesthesia. This may carry a risk of allergic reactions to anesthetics and other anesthesia-related risks for the subjects. Additionally, there may be restrictions on activities such as driving, cycling or working at heights on the day following the painless colonoscopy procedure.

8.1.2 Information confidentiality

The personal information and privacy of subjects involved in this trial will be protected and will not be disclosed. Any personally identifiable information of the subjects will be stored on a password-protected carrier that is accessible only to investigators at the participating clinical site where the subject is enrolled. Personally identifiable information includes, but is not limited to, the subject's name, identification number, social security account number, driver's license number, clinic number, hospitalization number, and any other information that directly or indirectly identifies the subject as an individual. Subject sample numbers will be assigned by the enrolled participating clinical site.

8.1.3 Subject benefits

Through enrolment in the study, subjects will receive 100 RMB as compensation for travelling expenses. Subjects will be offered a free fecal-based miR-92a test and FIT with result interpretation by a professional technician and possible follow-up management to improve knowledge of CRC prevention and early detection of possible risk of intestinal lesions.

Subjects will be offered a free colonoscopy if they have a positive fecal-based miR-92a test or FIT. If lesions are found, samples of the lesions will be taken for histopathology examination. Subjects can choose to undergo either plain or painless colonoscopy. The cost of colonoscopy (plain or painless) and histopathology examination will be borne by the company.

Subjects will be offered free colonoscopy when they have a negative fecal-based miR-92a test or a negative FIT test but are contacted by the investigator at random. If microscopic lesions are identified, they will be sampled for histopathology examination. Subjects may choose to undergo either a plain colonoscopy or a painless colonoscopy. The cost of colonoscopy (plain or painless) and histopathology examination will be borne by the company.

Subjects will not be offered a free colonoscopy if they have a negative fecal-based miR-92a test or a negative FIT test but are not contacted by the investigator at random.

8.1.4 Explanation of test safety

The use of fecal samples in this study does not pose any threat to the safety of the subjects.

8.2 Informed consent

The informed consent was strictly formulated in accordance with the relevant regulations and was submitted to the ethics review board for approval. Subjects have the right to review and comprehend the terms and conditions, as well as to ask questions regarding any of the terms and conditions. A copy of the informed consent will be given to the participant after he/she fully understands the content, risks and value of the study and signs it before enrolment in the study.

8.3 Data reliability

In this study, fecal-based miR-92a test and FIT will be done by professional technicians to ensure the accuracy of the sample laboratory test results. Colonoscopy will be performed by experienced endoscopists in strict accordance with the standard protocols for colonoscopy to avoid bias in the test results caused by human intervention. Subjects' colonoscopy and histopathological results will be entered and analyzed using clinical research database tools, so that the results will not be biased due to the researcher's subjective awareness.

8.4 Project management

Subject recruitment, sample collection and laboratory testing, colonoscopy and histopathology examination, and information collation will be controlled by the project investigators to ensure the proper functioning of the project. Confidentiality of information will be followed up and monitored by the head of the clinical site to ensure the proper conduct of the trial.

[figure not shown]
8.5 Ethics review committee

- Ethics review committee of Shenzhen People's Hospital (head unit) (Reference ID: SYL-202123-03);
- Ethics review committee of Shenzhen Bao'an District Hospital of Traditional Chinese Medicine (Reference ID: SJ-2021-001-04);
- Ethics review committee of Tianjin Nankai Hospital (Reference ID: NKYY YX IRB 2021 002).

9. Instructions for stool sample collection

- (1) Stool sample collection kit contains: sampling instructions, ice pack, sample tube, stool collection paper, self-sealing bag, insulated bag and disposable gloves.
- (2) The day before sampling, open the sample collection kit and take out the ice pack; open the water spout of the ice pack and fill it with tap water, gently squeeze out the excess air and close the water spout, then shake it well and put it into the freezer for more than 5 h. Women should avoid collecting fecal samples during their menstruation period, but can collect fecal samples before or after it.
- (3) When picking stool, open the package of plastic stool paper, tear off the protection paper of the adhesive strip on both sides of the stool paper, use the double-sided adhesive strip to fix the stool paper on both sides of the toilet ring, and make the middle of the stool paper downward to form a curvature. The plastic stool paper was used to collect the samples and avoid contamination with toilet water.
- (4) Defecation was performed at the curve of the stool collection paper. After completing defecation, the subject should wear disposable gloves, take out the sample tube and fill in the subject's name, subject number, and sampling time (e.g., 9:00 AM, May 18, 2021) in regular script on the label of the tube. Use the feces sampling spoon to scrape the feces from multiple points on the surface of the feces for no less than 6 times, with each scraping being the size of a broad bean and placing them at the bottom of the sample tube. If there are visibly identifiable food residues in the feces, such as watermelon seeds or corn kernels, the subject should avoid these areas when sampling and prevent food residues from entering the sample tube.
